8.5.2 Secondary analyses

- Per-protocol comparison of overall survival at 2 years
- ITT liver-progression-free survival,
- Rates of liver resection in HAI group compared with control group and with transplantation rate for TX group. Standard approximation to binary outcomes with Fisher exact test or chi-square.
- Quality-of-life as measured by EORTC-30

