Objectives	Main study objective: To improve treatment outcome for patients with a heavy burden of colorectal liver metastases and progression on 1 st line chemotherapy. Key secondary objectives: To establish whether the favourable results obtained by use of hepatic artery infusion chemotherapy can be replicated outside of US single centre series.
Endpoints:	Overall Survival (OS) at two years Secondary endpoints: Progression-free survival, overall survival at 5 years, resection/transplantation rate, quality of life.
Study Design:	Three-armed, two-sided, open label, parallel-group, single center, phase II trial.

Main Inclusion Criteria:	
– Multiple colorectal liver metastases (6 or more metastases)– Progression on 1st line chemotherapy
Main Exclusion Criteria	
– Extensive extrahepatic disease
Sample Size:	45 patients
Efficacy Assessments:	Overall survival, progression-free survival and resection rate
Safety Assessments:	Major adverse events/side-effects from chemotherapy and major complications following surgery.
Other Assessments:	Health economy assessment, quality-of-life

TABLE OF CONTENTS

CONTACT DETAILS	2
SIGNATURE PAGE	3
PROTOCOL SYNOPSIS	4
TABLE OF CONTENTS	6
1 INTRODUCTION	9
1.1 Background – Disease.....	9
1.2 Liver resections for Colorectal Liver metastases (CRLM).....	9
1.3 The grey zone.....	10
1.4 Systemic chemotherapy for CRLM.....	10
1.5 Liver transplant for CRLM.....	10
1.6 Hepatic artery infusion (HAI) chemotherapy for CRLM.....	10
1.7 Optimal treatment for patients with CRLM in the grey zone.....	11
1.8 Rationale for the Study and Purpose.....	11
1.9 Research hypothesis.....	11
2 STUDY OBJECTIVES AND RELATED ENDPOINTS	12
3 OVERALL STUDY DESIGN/OVERVIEW OF DESIGN	13
4 STUDY POPULATION	13
4.1 Selection of Study Population.....	13
4.2 Number of Patients.....	14
4.3 Inclusion and exclusion criteria.....	14
4.3.1 Inclusion Excalibur 1	14
4.3.2 Inclusion Excalibur 2	Feil! Bokmerke er ikke definert.
4.4 Exclusion Criteria.....	14
4.4.1 Exclusion.....	Feil! Bokmerke er ikke definert.
5 TREATMENT	15
5.1 Technical procedures.....	15
5.1.1 Second line systemic chemotherapy.....	15
5.1.2 Liver transplantation.....	15
5.1.3 Hepatic Artery infusion (HAI).....	16
5.1.4 Surgical procedure.....	16
5.2 Drug Accountability - IMP.....	20
5.3 Drug Labeling.....	20
5.4 Subject Numbering, different arms of the study.....	21
5.5 Schedule of events.....	21
5.6 By Visit.....	23

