2 STUDY OBJECTIVES AND RELATED ENDPOINTS

The objectives and endpoints of the study are listed in Table 1 below. The primary endpoint is Overall survival at 2 years after randomization. Safety and toxicity grade 3-5 toxicity will be reported.

Table 1 Objectives and related endpoint:

Objectives	Endpoints	Assessment
Primary: Overall survival	Overall survival at 2 years after randomization	Medical records
Secondary: 1. Efficacy	Overall survival (OS), at 5- and 10-years after randomization.	Medical records
Radiological response to treatment	Response rate	CT/MRI-scans RECIST 1.1
2. Efficacy	Resection rate	Medical records
3. Efficacy	Number of patients randomized til HAI receiving HAI-treatment	
4. Efficacy	Quality of life	EORTC QoL C30
Safety all patients	Adverse events in patients receiving chemotherapy	NCI-CTC 5.0 grade III-V toxicity
Safety in patients receiving resection/transplantation.	Major surgical complications	Accordion Grade III - VI
Exploratory	Molecular analyses related to disease-free and overall survival	Biobank stored blood and tumour tissue
	Progression free survival (PFS). (PFS will be calculated both with and without sensing patients receiving resection or transplantation at time of resection/transplantation) Disease free survival after liver resection/transplantation in the different treatment arms	CT/MRI-scans RECIST 1.1

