5 TREATMENT

For this study the drugs that are used for HAI are fluorodeoxyuridine also known as floxuridine (FUDR, Fresenius Kabi, LLC, USA) and dexamethasone. These drugs are defined as Investigational Medicinal Product (IMP). The patients will receive 20 mg proton pump inhibitor.

All patients will receive second line standard systemic chemotherapy at the discretion of the treating medical oncologist. Resection in the HAI and standard care groups will be undertaken only provided sufficient response on 2nd line chemotherapy (with or without HAI/FUDR) has been achieved (defined as ≥ 10 % response on median diameter of two target lesions, i.e. measured as with RECIST 1.1. but with a trial-specific cut-off). The study is a three- armed study, where the control arm receives systemic 2nd line chemotherapy only, one arm receive systemic chemotherapy and HAI and the third arm 2nd line systemic chemotherapy and liver transplantation.

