 - Monthly pregnancy testing should be performed in women of childbearing potential (WOCBP) as long as they receive chemotherapy according to study protocol. This can be done with a urine test at home combined with contact with the study team by phone
 - A calendar for oncologist visits and provision of systemic chemotherapy is created by coordinating nurse. Control scans are ordered for each 2nd month for the first year following randomization and as long as the patients receive chemotherapy, each 3rd month for the second year and each 6th month for the third year. MDT meetings are scheduled for one week following each new scanning to assess response and possible resectability
 - Out-patient control appointments are scheduled for outcome assessment including QoL-scoring (3, 6, 9, 15, 18, 21 and 24 months)
- Patients in HAI group (group 2 a and 2b)
 - A calendar of reservoir refills is created and harmonized with provision of systemic treatment.
 - A laparotomy is performed within 2 weeks from randomization with insertion of catheter and reservoir for HAI-pump.
- Patients in transplant group
 - Oncologists are instructed to avoid Avastin in systemic chemotherapy while the patient is listed.

Table 3: Overview of screening procedures, End of study/Withdrawal

Overview of screening procedures, End of study Withdrawal												
Item	ICF	Inc/Ex	Med Hist	Prior Trea	Phys Exam	Vit Sign	ECOG	CT/ MR	QoL	Blood Sample	Adverse Event	Survival Assessment
Screening	x	x	x	x	x	x	x	x	x	x	x	
EOS/Withdrawal											x	x

Table 4: Calendar of cycles and events for patients in HAI group

Calendar of cycles and events for patients in HAI group								
Day cycle 1 + 2	1	2	15	16	29	30	44	
Day cycle 3 + 4	61	62	75	76	89	90	104	
Pump refill FUDR at OUS	x				x			
Pump refill HepNaCl at OUS			x					x
Systemic chemo local hospital		x		x		x		

Table 5: Calendar of cycles and events for patients in control group and on waiting list for LTx-group

Calendar of cycles and events for patients in control group and on waiting list for LTx- group							
Day cycle 1 + 2	1		15		29		44
Day cycle 3 + 4	61		75		89		104
Systemic chemo local hospital	x		x		x		x

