5.6.5 After End of Treatment (Follow-up)

Patients having a liver resection or liver transplantation will have follow-up according to Table 6-7. These patients will have follow-up until 10 years after surgery or until they start palliative treatment.

Table 6. Follow-up of resected Excalibur study patients

Follow up Ltx patients	Visits 1 st year (every month)	Visits 2 nd year (every 3 month)	Visits 3 rd -10 th years (every 6 month)
Hb CRP, Hv, Trc, Na, K, Crea	X	X	X
Bilirubin, ASAT, ALAT, ALP, Alb	X	X	X
INR, Cholesterol, glucose, HbA1c	X	X	X
CEA, CA 19-9,	Every 3 months	X	X
TIMP-1, TPA (stop at relapse)	Every 3 months	X	X
5 ml EDTA plasma for later analyses (until relapse)	Every 3 months	X	X
5 ml serum for later analyses (until relapse)	Every 3 months	X	X
Weight	X	X	X

BP	X	X	X
CT thorax/abdomen/pelvis (only in Ltx patients without relapse)	Every 2 months	Every 3 months	Every 6 months
US Liver w/Doppler (only Ltx patients)	Every 3 months		
Coloscopy (only in Ltx patients without relapse)	At 12 months	At 36 months	At 60 months
PET scan (only in patients without lesions on CT)	At 12 months	At 24 months	
EORTC QLQ-C30 and EQ5D	3, 6, 12, months	2 times/year	2 times 3.year

Table 7 Follow-up of Control group, HAI-group and patients not receiving LTx

arm		Outcome	Palliative treatment	Follow Up
3 and 2	Chemo therapy	Surgery	No	10 Years
	FUDR/HAI	PD/Toxicity	yes	Will do "End of treatment visit". OS will be collected.
1	Liver Tx	Transplant	No	10 Years.
		Extra-hepatic disease	yes	Will do "End of treatment visit". OS will be collected.
		Metastasis to lymphnodes	yes	Will do "End of treatment visit". OS will be collected.

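### Secondary analyses: resection rate is tested against transplantation rate, liver-PFS is listed nowhere else, and two quality-of-life calendars conflict

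*Protocol*

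**What the plan says.** **Resection and transplantation.** Section 8.5.2 lists "Rates of liver resection in HAI group compared with control group and with transplantation rate for TX group", and adds "Standard approximation to binary outcomes with Fisher exact test or chi-square". Section 5 states that "Resection in the HAI and standard care groups will be undertaken only provided sufficient response on 2nd line chemotherapy", with a trial-specific cut-off of at least 10 % on the target lesions. Transplantation is the allocated treatment of group 1, and section 5.6.3 keeps a patient listed after progression.

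**Progression.** The synopsis gives "Secondary endpoints: Progression-free survival, overall survival at 5 years, resection/transplantation rate, quality of life". Table 1 in section 2 puts PFS in the exploratory block and says that "PFS will be calculated both with and without sensing patients receiving resection or transplantation at time of resection/transplantation" (evidently meaning censoring). Section 8.5.2 instead names "ITT liver-progression-free survival", without a rule for a resected or removed liver. Section 5.10 describes tumour response assessment before resection or transplantation only.

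**Quality of life.** Section 5.5, under the items for all patients, has "Out-patient control appointments are scheduled for outcome assessment including QoL-scoring (3, 6, 9, 15, 18, 21 and 24 months". In section 5.6.5, Table 6 has a row "EORTC QLQ-C30 and EQ5D" set at 3, 6 and 12 months, then twice a year. This belongs to the follow-up of operated patients, which runs to 10 years after surgery or until palliative treatment starts. Table 7 gives patients with progression or toxicity, and transplant-arm patients who go to palliative treatment, an end-of-treatment visit and collection of OS.

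**The concern.** A secondary comparison between randomised arms should measure the same thing, at the same times, in each arm. Three of those planned here do not clearly do so.

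- The transplantation rate records whether the allocated treatment was delivered. The resection rate in the HAI arm records whether treatment converted the patient to operability. A small p-value between them could be reported as a finding about efficacy when it is not one.
- Once the native liver is removed, the metastases that define liver progression are gone. Liver-PFS then means something different in the transplant arm from what it means in the other two. It is also unclear which PFS is the secondary endpoint, because three places in the protocol give three answers.
- If quality of life is collected on one calendar in operated patients and another in the rest, and possibly not after progression, the arms would be compared at different times and in differently selected patients. Questionnaires not collected cannot be recovered by a later analysis plan.

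**Working it through.** **1. Resection against transplantation**

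The protocol gives no sample size or power for this comparison, so the group sizes come from section 8.1. They reproduce with unpooled variances, two-sided 5 % and 80 % power, where (1.95996 + 0.84162)² = 7.849:

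- HAI versus control, 75 % against 30 %: 7.849 × (0.21 + 0.1875) / 0.45² = 15.4, so 16 per group.
- Transplant versus control, 90 % against 30 %: 7.849 × (0.21 + 0.09) / 0.60² = 6.54, so 7.
- 16 + 16 + 7 = 39, and 39 × 1.15 = 44.85, so 45, split 18 + 18 + 9.

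Now suppose 8/18 HAI patients are resected (44 %, near the 23/49 = 47 % and 33/64 = 52 % in the two HAI series cited in section 1.6) and all 9 transplant patients are transplanted. With 17 operated among 27, Fisher's test gives:

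- Probability of the observed table: C(17,9) / C(27,9) = 24,310 / 4,686,825.
- Tables no more likely have 0, 1 or 2 transplanted, with counts 10, 765 and 16,320.
- p = (24,310 + 10 + 765 + 16,320) / 4,686,825 = 41,405 / 4,686,825 = 0.009.

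With 8/9 transplanted p = 0.042, and with 7/9 p = 0.22. The exact probability that Fisher's test rejects at 5 % with 18 against 9 patients is below. The transplantation rates and the 30 % resection rate are assumptions, and the 18 counts HAI patients of both sub-trials.

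| HAI resection rate | TX rate 80 % | TX rate 90 % | TX rate 95 % |
|---|---|---|---|
| 30 % | 0.698 | 0.889 | 0.955 |
| 47 % | 0.326 | 0.553 | 0.690 |
| 52 % | 0.234 | 0.432 | 0.564 |

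An ordinary HAI result and good delivery of transplants could therefore easily give a significant test that says nothing about which treatment works better. Table 1 already contains the natural counterpart of the transplantation rate: the number randomised to HAI who receive it, which is also a measure of delivery.

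**2. Progression**

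| Place | Endpoint | Status |
|---|---|---|
| Synopsis | PFS | secondary |
| Table 1 | PFS, with and without censoring at surgery | exploratory |
| Section 8.5.2 | liver-PFS, ITT | secondary analysis |

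No two rows agree on both endpoint and status.

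**3. Quality of life**

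- Year 1 as printed: months 3, 6, 9 (section 5.5) against 3, 6, 12 (Table 6). Only 3 and 6 are shared.
- Years 1 and 2, if twice a year means months 18 and 24 (assumption): 3, 6, 18 and 24 are shared; 9, 15 and 21 stand only in section 5.5; 12 stands only in Table 6.
- If Table 6 counts from surgery and section 5.5 from randomisation, the match depends on the delay to surgery. At 1, 2 or 4 months no time point coincides. At 3 months, months 6, 9, 15 and 21 do. At 6 months, months 9, 18 and 24 do.

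The delay will vary between patients, so no fixed set of common time points can be relied on.

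**The case against.** **Resection against transplantation.** Transplantation is not automatic: listing needs MDT agreement (section 5.1.2), and Table 7 foresees transplant-arm patients who go to palliative treatment instead. The synopsis pairs the two rates, which can be read as the share reaching surgery. The rationale calls the transplant arm a benchmark, and section 8.1 says that HAI against transplant is not powered. This stands to the extent that the comparison is not devoid of all meaning. It still does not measure relative efficacy, and a printed significance test invites that reading.

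**Progression.** The event definition for liver-PFS can be left to the SAP. Extrahepatic progression is captured by PFS and by disease-free survival after surgery. Both are true, but a SAP detail does not settle a conflict over status and endpoint inside the protocol.

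Stronger readings are tempting, and the documents do not support them:

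- A reader might fault the PFS version censored at surgery. Table 1 plans it beside the uncensored version, in an exploratory row, so it is not an error.
- A reader might put a hazard ratio on the liver-PFS problem by taking one minus the hepatic share of first progressions. That formula describes progression at any site, not liver-PFS. It also ignores the wait before transplantation, and the protocol gives no hepatic share.
- A reader might infer that these analyses favour HAI by construction. Resection rate and liver-PFS are like-for-like between HAI and control.
- A reader might infer that quality of life is scheduled differently by randomised arm. Section 5.5 covers all patients, and Table 6 follows surgery status, whatever the arm. Nothing says that Table 6 replaces section 5.5, the origin of the months in section 5.5 is not stated, and Table 7 does not say that questionnaires stop.

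**Conclusion.** The point holds in three limited parts, all on secondary or exploratory outcomes.

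1. The test of HAI resection against transplantation is fixed in the text and cannot be read as relative efficacy. The p = 0.009 for 8/18 against 9/9 is an illustration, not a forecast. The HAI versus control half of the same sentence is sound.
2. The status and definition of PFS conflict across the synopsis, Table 1 and section 8.5.2. Liver-PFS is not comparable for the transplant arm after the native liver is removed. No size can be put on this from the documents.
3. The quality-of-life calendars conflict on month 12 and, it appears, on time origin, and collection after progression is left in doubt. Most transplant-arm patients should be operated on, so the effect would fall unevenly by arm. Its direction is unknown.

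The primary analysis of overall survival is unaffected. This should be corrected, but it does not threaten the trial's main result.

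**What to change.** - **Section 8.5.2, rates:** test the resection rate for HAI versus control only. Report the transplantation rate descriptively, for example beside the number of HAI patients who received HAI.
- **Synopsis, Table 1 and section 8.5.2, progression:** name one secondary PFS in all three: RECIST 1.1 progression at any site, or death, by ITT and without censoring at surgery. Table 1 already plans that version; the censored version can stay exploratory. State in section 5.10 that relapse after surgery counts as an event. Limit liver-PFS to HAI versus control, and list it in Table 1 if it is kept.
- **Section 5.5 and Tables 6 and 7, quality of life:** reconcile these into one calendar counted from randomisation, the same for every patient, including month 12 and continued after progression or toxicity.

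The first two changes cost only wording. The third adds some questionnaires per patient, including after progression in patients treated at local hospitals, so a way of collecting them there must be arranged. It has to be made in the protocol, before those time points pass.

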8 STATISTICAL METHODS AND DATA ANALYSIS

8.1 Determination of Sample Size

We estimate an overall survival at two years in the standard care group (group 3) to be 30 %. We aim to decide whether the use of HAI (group 2) can increase this to 75 % and if liver-TX (group 3) can increase this to 90 %. For a two-sided parallel-group test of proportions to answer both questions with a power of 0.80 and an alpha of 0.05, this will require 16 completed patients per group 3 and 2 to show superiority for HAI over standard care (systemic chemotherapy). An additional 7 patients is needed in the transplant group (1) to show superiority over standard care group (3), bringing the total to 39 patients. This is based on a three-year accrual time, and a total of five-year follow-up from the first patient, ensuring at least two years follow-up for all patients. The trial is not powered to show a difference between group 2 and 1. Adding 15 % to allow for drop-outs, we aim to randomise a total of $18 + 18 + 9 = 45$ patients in a 2:2:1 ratio.

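### Section 8.5.2 leaves the resection-rate test open between Fisher and chi-square; at about 18 per arm the choice can decide significance, so one test should be named

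*Protocol*

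**What the plan says.** Section 8.5.2 of the Protocol lists this secondary analysis: "Rates of liver resection in HAI group compared with control group and with transplantation rate for TX group". The method given for it is "Standard approximation to binary outcomes with Fisher exact test or chi-square". So one sentence covers two comparisons: HAI v control on resection, and resection on HAI v transplantation in the transplant (TX) arm. It does not say which test applies when, or whether chi-square carries a continuity correction. It also describes the pair as an approximation, although Fisher's test is exact.

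Section 8.1 gives the arm sizes. The sponsor writes "we aim to randomise a total of" 45 patients: 18 on HAI, 18 on control and 9 to transplantation. The 5% two-sided level appears there, for the survival comparison: "For a two-sided parallel-group test of proportions to answer both questions with a power of 0.80 and an alpha of 0.05".

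Resection rate is a secondary efficacy endpoint in the synopsis and in Table 1. Section 10 includes more patients reaching resection in the trial's hypothesis. The synopsis describes the design as open-label. Section 8.4 defers further detail to a separate statistical analysis plan (SAP), to be signed before database lock.

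**The concern.** In large samples the two named tests give nearly the same answer and an either/or does little harm. With 18 per arm they do not. One is clearly conservative, and the other, uncorrected, can run above its nominal level. A band of quite plausible results is significant by one and not by the other.

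Because the trial is open-label, resection counts by arm can be known while the choice is still open; the SAP need only be final by database lock. What is at stake is the claim that HAI brings more patients to resection.

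**Working it through.** **Inputs**
- Arms of 18, 18 and 9: section 8.1.
- Two-sided 5%: stated in section 8.1 for survival; carrying it over to this endpoint is an assumption.
- Resection rate on HAI: 23/49 = 47%, from the first series cited in section 1.6. The second series there gives 33/64 = 52%.
- Resection rate on control: not given in the Protocol. Assumed 10% to 20%, with 5% also shown.

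**The plan's own figure.** There is no calculation for resection, but the arm sizes reproduce. With n = (1.960 + 0.842)² × [p₁(1−p₁) + p₂(1−p₂)] / (p₁−p₂)² and (1.960 + 0.842)² = 7.849:
- 30% v 75%: 7.849 × (0.21 + 0.1875) / 0.2025 = 15.4, so 16 per group.
- 30% v 90%: 7.849 × (0.21 + 0.09) / 0.36 = 6.5, so 7.
- 16 + 16 + 7 = 39, and 39 × 1.15 = 44.9, so 45.

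**Error rates at 18 v 18.** There are 19 × 19 = 361 possible outcomes. Each has probability Bin(a; 18, p₁) × Bin(b; 18, p₂). Summing over the outcomes each test rejects at p ≤ 0.05, with p₁ = p₂, gives the true size. Boschloo's test orders outcomes by the two-sided Fisher p-value and takes the largest cut that keeps the maximum size within 5%; here the cut is Fisher p ≤ 0.088.

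| Test | Maximum size | At 10% | At 15% | At 20% | At 50% |
|---|---|---|---|---|---|
| Fisher | 2.9% | 0.9% | 1.7% | 2.1% | 2.9% |
| Chi-square, uncorrected | 6.5% | 3.3% | 4.6% | 4.8% | 6.5% |
| Chi-square, Yates | 2.9% | 0.3% | 0.9% | 1.5% | 2.9% |
| Boschloo | 4.8% | 1.2% | 2.9% | 4.0% | 3.9% |

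**Power and disagreement, 47% on HAI**

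| Control rate (assumed) | Fisher | Uncorrected chi-square | Boschloo | Fisher and uncorrected chi-square disagree |
|---|---|---|---|---|
| 5% | 0.79 | 0.88 | 0.87 | 8.6% |
| 10% | 0.60 | 0.72 | 0.72 | 12.7% |
| 15% | 0.43 | 0.57 | 0.56 | 13.9% |
| 20% | 0.29 | 0.42 | 0.40 | 13.1% |

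With equal true rates the two disagree in at most 3.6% of trials. Fisher and Yates disagree in under 1% at control rates of 10% to 20%.

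**Example: 9/18 v 3/18**
- Uncorrected: χ² = 36 × (9×15 − 9×3)² / (18 × 18 × 12 × 24) = 36 × 108² / 93,312 = 4.50, p = 0.034.
- Yates: 36 × (108 − 18)² / 93,312 = 3.125, p = 0.077.
- Fisher: 2 × 46,960,290 / 1,251,677,700 = 0.075.
- Boschloo: 0.038. The scipy routine takes the arms as columns; entering them as rows conditions on the wrong margin and returns 0.044.

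This is not a lone case. For every control count from 2 to 10, six more resections on HAI gives p < 0.05 by uncorrected chi-square and p > 0.05 by Fisher (8 v 2: 0.026 and 0.060; 12 v 6: 0.046 and 0.094).

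**Other arm sizes.** Maximum size at 16 v 16: Fisher 2.0%, uncorrected chi-square 5.8%, Boschloo 4.1%. At 18 v 9, the second comparison: 3.9%, 6.3% and 4.8%.

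**The case against.** The strongest reply is that choosing between two conventional tests for a secondary endpoint is the kind of detail an SAP settles, and section 8.4 promises one. That carries weight and is a main reason to rate the point low. It does not remove it: the Protocol addresses the test and fixes it as an either/or, and the SAP may be signed after resection counts are visible.

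The second reply is that the gap depends on which chi-square is meant. This stands. If the sponsor intends the continuity-corrected form, the conflict with Fisher almost disappears, as the example shows. The Protocol does not say which it intends.

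Third, exactly 18 v 18 is not assured. Section 8.2.1 allocates 1:1:1 in Excalibur 1 and 1:1 in Excalibur 2, so 18/18/9 arises only if 27 patients enter the first (9 + 9 + 9) and 18 the second (9 + 9). The gap between the tests nevertheless persists at 16 v 16.

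A reader might also infer more than the document supports:
- That neither test is sound. Fisher never exceeds 5%; low power is inefficiency, not invalidity.
- That chi-square would run at 6.5% here. That is the worst case, near a 50% common rate; at 10% to 20% the uncorrected test stays below 5%.
- That the tests conflict in one trial in seven regardless. That holds only for true differences of roughly 30 points.

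**Conclusion.** The point holds, as a minor one. Section 8.5.2 leaves open a choice that can decide significance at the planned arm sizes. If HAI reaches 47% and control 10% to 20%, the two tests disagree in about 13% to 14% of trials (8.6% with control at 5%, at most 3.6% with no true difference).

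This rests on uncorrected chi-square, arms of 18 v 18, a two-sided 5% level carried over from section 8.1, and control rates that are assumed. The primary analysis is overall survival by Cox regression and is not affected, so nothing here bears on the trial's main conclusion.

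**What to change.** In section 8.5.2, replace the either/or with one named test for both comparisons in that sentence (HAI v control on resection, and HAI resection v TX transplantation): Boschloo's unconditional exact test, two-sided 5%, on all randomised patients at the realised arm sizes. Define the two-sided version as ordering outcomes by the two-sided Fisher p-value; it then rejects whenever Fisher does, so it is never less powerful. Report the risk difference with a 95% interval, exact unconditional or Newcombe, and state that the test governs, since test and interval need not agree at the margin.

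The gain over Fisher at 18 v 18 is 0.72 − 0.60, 0.56 − 0.43 and 0.40 − 0.29 for control at 10%, 15% and 20%: about 11 to 13 points of power, with size still at most 4.8%.

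The cost is one sentence, and the test is in standard software. There are two downsides. The test is less familiar. It is also unstratified, whereas section 3 describes the pooled HAI v control comparison as stratified for age and primary tumour status. If the sponsor prefers Fisher, naming it alone would still close the open choice, at the price of that power.
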